10.2.2 Adverse Event Overview

An overview of AEs will be presented consisting of the number and percentage of subjects experiencing at least one event for each of the following AE categories:

- Any TEAE
- Any TEAE related to COVID-19
- Any TEAE that was rated as with reasonable possibility to study drug by the investigator.
- Any TEAE with CTCAE grade ≥ 3
- Any serious TEAE.
- Any TEAE leading to discontinuation of study drug.
- Any TEAE leading to death.
- Treatment-emergent AESI (See ABBV-154 Product Safety SAP (PSSAP) for details).
- All deaths
 - Deaths occurring ≤ 70 days after last dose of study drug
 - Deaths occurring > 70 days after last dose of study drug
 - Deaths related to COVID-19

In addition, an overview of AEs per 100 patient-years of study exposure will be presented for the AE categories defined above. The number of TEAEs reported, the total number of years of study drug exposure, and the TEAE rate per 100 patient-years will be presented.

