7.7 Statistical Analyses for Safety

All safety analyses will be performed using the Safety Population, as defined in Section 7.2. Data will be analyzed based on the actual treatment subjects received. TEAEs, laboratory assessments, and vital signs will be summarized. Details will be described in the SAP.

A TEAE for the Safety Population is defined as an AE newly occurred or worsened after the first dose of study drug and within 70 days after the last dose of study drug. The number and percentage of subjects experiencing TEAEs will be tabulated using the Medical Dictionary for Regulatory Activities (MedDRA) system organ class and preferred term, by severity, and by relationship to the study drug as assessed by the investigator. Summaries (including percentages and events per 100 patient years) of SAEs, deaths, and AEs leading to discontinuation will also be provided. Procedure related pretreatment AEs will be summarized separately.

For selected laboratory parameters, a listing of all subjects with any laboratory value that is Grade ≥ 3 of NCI CTCAE will be provided. Mean change in laboratory and vital signs variables will be summarized. Additional details for the safety analysis will be provided in the SAP.

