10.2.4 Treatment-Emergent Adverse Events per Patient-Years of Exposure

TEAEs will be summarized by event rate per 100 subject years, defined as

$$100 \times \frac{\text{Number of TEAEs}}{\text{Total Patient Years}}$$

where total patient years is defined as the sum of the study drug exposure of all subjects, normalized by 365.25, and rounded to 1 decimal place. Note that one event per preferred term per day per subject will be counted in the calculation of the number of AEs (i.e., a preferred term will not be counted twice on the same day for the same subject).

The TEAE rates per 100 patient-years of exposure will be provided for each AE category in the AE overview summary (defined in Section 10.2.2) and for TEAE summary by SOC and PT.

The study drug exposure for each safety population is defined as last dose date plus 70 days, minus the first dose date. For SA-All154 safety population, the duration when subjects on Placebo will not be included in the calculation.

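### The SAP asks for a rate per 100 patient-years for deaths more than 70 days after last dose, but its only exposure denominator closes at 70 days, so that row has no valid rate

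*SAP*

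**What the plan says.** SAP 10.2.2 sets out the categories of the adverse event overview. Most are treatment-emergent. The last is all deaths, with three sub-rows: deaths up to 70 days after the last dose, "Deaths occurring > 70 days after last dose of study drug", and deaths related to COVID-19. The all-deaths and COVID-19 rows carry no time limit.

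The same section then asks for rates: "In addition, an overview of AEs per 100 patient-years of study exposure will be presented for the AE categories defined above". SAP 10.2.4 repeats the requirement: "The TEAE rates per 100 patient-years of exposure will be provided for each AE category in the AE overview summary". Neither sentence leaves out the death rows.

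The denominator is defined once: "The study drug exposure for each safety population is defined as last dose date plus 70 days, minus the first dose date". These times are then added over subjects, divided by 365.25 and given to one decimal.

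The numerator is worded only for treatment-emergent events: "The number of TEAEs reported, the total number of years of study drug exposure, and the TEAE rate per 100 patient-years will be presented". Protocol 7.7 defines such an event thus: "an AE newly occurred or worsened after the first dose of study drug and within 70 days after the last dose of study drug". That protocol section also asks for deaths to be summarised with events per 100 patient-years.

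**The concern.** A death more than 70 days after last dose falls, by definition, after the denominator has closed. The SAP requires a rate for that row but provides neither a numerator that covers it nor a denominator that contains it. Two programmers following the text could produce different tables, and neither table would show a meaningful late-death rate. The all-deaths and COVID-19 rows take on the same problem for any late death they include.

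Late deaths can come to light. Protocol 5.6 encourages subjects who stop study drug to keep attending scheduled visits, and it allows survival status to be taken from public records for those who withdraw. The SAP itself provides a row for them. Death rates for a conjugate of an anti-TNF antibody and a glucocorticoid receptor modulator will be read closely, so the printed figure should mean what its label says.

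**Working it through.** The documents state no death rate or patient-year total, so there is no printed figure to reproduce. The check applies the SAP formula.

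**Windows**
- Denominator (SAP 10.2.4): first dose to last dose + 70 days.
- Late-death row (SAP 10.2.2): after last dose + 70 days.
- Overlap: 0 patient-years, whatever the number of events or discontinuations.

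**Two readings of the numerator**
- Strict (treatment-emergent events only): a death after day 70 is not itself inside the window, so the row is zero or has no defined rate even if such deaths occur. If the fatal event began inside the window, it already counts in the row for treatment-emergent events leading to death. The SAP does not say whether it should also count here.
- Broad (count the deaths in the row): rate = 100 × deaths / patient-years, where no part of the patient-years is time at risk.

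**Size under the broad reading, fully dosed arms**
- Induction: 53 per group (SAP 2.4), last dose at Week 10 = day 70 (SAP 2.2). 53 × (70 + 70) / 365.25 = 20.3 patient-years. One late death: 100 / 20.3 = 4.9 per 100 patient-years.
- Maintenance: 40 per group (SAP 2.4), last dose at Week 38 = day 266 (SAP 2.2). 40 × (266 + 70) / 365.25 = 36.8 patient-years. One late death: 100 / 36.8 = 2.7 per 100 patient-years.

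**Effect of discontinuation (assumed, not in the documents)**

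Take a Maintenance arm of 40. Between 10% and 50% stop drug, with last dose between day 0 and day 140, and are followed to day 280. The rest complete, with 336 days each.

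| Stop drug | Last dose | SAP exposure (patient-years) | Time after day 70 (patient-years) | One late death, SAP denominator | One late death, all observed time |
|---|---|---|---|---|---|
| 10% (4) | day 140 | (4 × 210 + 36 × 336) / 365.25 = 35.4 | 4 × 70 / 365.25 = 0.77 | 2.8 | 2.8 |
| 50% (20) | day 0 | (20 × 70 + 20 × 336) / 365.25 = 22.2 | 20 × 210 / 365.25 = 11.5 | 4.5 | 3.0 |

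The last two columns are per 100 patient-years. Over these assumptions, the contribution of one late death to the all-deaths rate runs from nearly the same on both denominators to about 1.5 times as large (4.5 / 3.0). Divided only by the time in which a late death could occur, the same single death would give about 9 (100 / 11.5) to 130 (100 / 0.77) per 100 patient-years. The late-death figure from the SAP denominator therefore does not estimate the late-death rate.

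**The case against.** The strongest reply is that both rate passages name treatment-emergent events as the numerator. On that reading late deaths never enter the table, nothing is inflated, and numerator and denominator share the same 70-day limit. This is a fair reading of the formula, and it rules out saying as fact that the all-deaths rate will be overstated. It does not settle the matter, because both sections still ask for a rate in every overview category. Strict application leaves the late-death row at zero or blank even when late deaths have been recorded, and the SAP does not say which reading is meant.

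A reader might also infer that time at risk is understated several-fold, for example for a subject who stops after one Induction dose and is then followed for a year. The documents do not provide that follow-up. Scheduled Induction visits end at Week 12, and entry to later periods is by re-randomization or assignment to study drug, so the supported ratio is 84 / 70 = 1.2. A subject who stops after one Maintenance dose and is followed to Week 40 gives 280 / 70 = 4, but that is one extreme subject and not an arm-level rate.

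It also stands that the overview gives n (%) for every row, separates early from late deaths, and includes treatment-emergent events leading to death. No primary or secondary result is affected.

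**Conclusion.** The point holds as a defect in a descriptive safety table. The row for deaths beyond 70 days has no valid rate under either reading, and this follows from the definitions alone. The all-deaths and COVID-19 rows are mismatched only to the extent that they include late deaths.

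The 4.9 per 100 patient-years in a fully dosed Induction arm is an illustration. It assumes that late deaths are counted and that all 53 subjects receive every dose. The arm-level distortion of the all-deaths rate is likely small. It depends on discontinuation and on the number of late deaths, neither of which the documents project. The documents do not support a stronger claim of systematic inflation or of a several-fold error. The rate for deaths within 70 days matches its denominator and can stand.

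**What to change.** In SAP 10.2.2 and 10.2.4, state that rates per 100 patient-years apply only to the treatment-emergent categories and to deaths up to 70 days after last dose. Report all deaths, deaths beyond 70 days, and COVID-19 deaths without a 70-day limit as n (%) only. The rate for deaths within 70 days supplies the exposure-adjusted death summary that Protocol 7.7 requires. The change also fits SAP 10.3 and 10.4, which already exclude laboratory and vital-sign data collected more than 70 days after last dose.

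A rate over total follow-up is not a clean substitute. Routine adverse event collection ends at 70 days (Protocol 6.1), and public-record survival checks are optional, so deaths and observed time would not clearly match.

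The cost is a clarifying sentence in each section and the loss of two or three rate cells. No new data are needed and trial conduct does not change.

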10.2.3 Treatment-Emergent Adverse Events by SOC and/or PT

TEAEs will be summarized by SOC and PT; by maximum relationship to study drug as assessed by the investigator (e.g., reasonable possibility or no reasonable possibility) and SOC and PT; by maximum severity and SOC and PT; and by subject number and SOC and PT. Specific AEs will be counted once for each subject for calculating percentages, unless stated otherwise. In addition, if the same AE occurs multiple times within a subject, the highest severity and level of relationship to investigational product will be reported. The SOCs will be presented in alphabetical order, and the PTs will be presented in alphabetical order within each SOC.

For summary by maximum severity, if a subject has an AE with an unknown severity, then the subject will be counted in the severity category of unknown, even if the subject

has another occurrence of the same event with a severity present. The only exception is if the subject has another occurrence of the same AE in the same analysis period with grade ≥ 3 . In this case, the subject will be counted under the maximum AE grade.

For summary by maximum relationship to study drug, if a subject has an AE with an unknown relationship, then the subject will be counted in the relationship category of "unknown," even if the subject has another occurrence of the same event with a relationship present. The only exception is if the subject has another occurrence of the same AE in the same analysis period with a relationship assessment of "Reasonable Possibility." In this case, the subject will be counted under the "Reasonable Possibility" category.

In addition, TEAEs will be summarized by PT and sorted by decreasing frequency for the total ABBV-154 group.

10.2.4 Treatment-Emergent Adverse Events per Patient-Years of Exposure

TEAEs will be summarized by event rate per 100 subject years, defined as

$$100 \times \frac{\text{Number of TEAEs}}{\text{Total Patient Years}}$$

where total patient years is defined as the sum of the study drug exposure of all subjects, normalized by 365.25, and rounded to 1 decimal place. Note that one event per preferred term per day per subject will be counted in the calculation of the number of AEs (i.e., a preferred term will not be counted twice on the same day for the same subject).

The TEAE rates per 100 patient-years of exposure will be provided for each AE category in the AE overview summary (defined in Section 10.2.2) and for TEAE summary by SOC and PT.

The study drug exposure for each safety population is defined as last dose date plus 70 days, minus the first dose date. For SA-All154 safety population, the duration when subjects on Placebo will not be included in the calculation.

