6.0 Study Drug Duration and Compliance

For the safety populations (SA1, SA2 and SA3), duration of treatment will be summarized by each treatment group for each period. Duration of treatment is defined for each subject as last dose date of blinded study drug minus first dose date + 14. Duration of treatment

will be summarized for each treatment group using the number of subjects treated, mean, standard deviation, median, minimum, and maximum. In addition, the number and percentage of subjects in the following treatment duration intervals will be summarized.

Induction/Re-Induction Period: < 2 weeks [14 days], ≥ 2 weeks [14 days], ≥ 4 weeks [28 days], ≥ 8 weeks [56 days], and ≥ 12 weeks [84 days]

Maintenance Period: < 2 weeks [14 days], ≥ 2 weeks [14 days], ≥ 4 weeks [28 days], ≥ 8 weeks [56 days], ≥ 12 weeks [84 days], ≥ 24 weeks [168 days], ≥ 36 weeks [252 days], and ≥ 40 weeks [280 days]

Treatment compliance will be summarized by treatment group for each period for the safety population. Treatment compliance is defined as the number of infusions/injections actually taken divided by the number of infusions/injections that should have been taken. Percent compliance will be summarized.

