10.2.1 Treatment-Emergent Adverse Events

Induction Period (SA1 population): TEAEs for the Induction Period are defined as events that begin either on or after the first dose of the study drug in the Induction Period and until (i) the first dose of study drug in the Re-Induction Period (if applicable), or (ii) until first dose of study drug in the Maintenance Period (if applicable), or (iii) within 70 days after the last dose administration of the study drug in the Induction Period, whichever is earlier.

Re-Induction Period (SA2 population): TEAEs for the Re-Induction Period are defined as events that begin either on or after the first dose of the study drug in the Re-Induction Period and until (i) first dose of study drug in the Maintenance Period (if applicable), or (ii) within 70 days after the last dose administration of the study drug in the Re-Induction Period, whichever is earlier.

Maintenance Period (SA3 population): TEAEs for the Maintenance Period are defined as events that begin either on or after the first dose of the study drug in the Maintenance Period and until (i) within 70 days after the last dose administration of the blinded study drug in the Maintenance Period, or (ii) initiation of ABBV-154 rescue therapy, whichever is earlier.

ABBV-154 Rescue Therapy (SA-RES population): TEAEs for the ABBV-154 rescue therapy are defined as events that begin either on or after the first dose of the ABBV-154 rescue therapy in the Maintenance Period and until 70 days after the last dose administration of the study drug in the Maintenance Period.

All ABBV-154 (SA-ALL154 population): TEAEs for "All ABBV-154" are defined as events that begin either on or after the first dose of ABBV-154 and within 70 days after the last dose of ABBV-154 in the study. Events that begin when subjects on Placebo will be not included.

Safety analyses from combined periods:

Induction Period + Re-Induction Period ABBV-154 (SA-IN2 population): TEAEs for "Induction Period + Re-Induction Period ABBV-154" (SA_IN2) are defined as events that begin either on or after the first dose of ABBV-154 in the Induction Period and until (i) first dose of study drug in the Maintenance Period (if applicable), or (ii) within 70 days after the last dose of study drug in the study, whichever is earlier.

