Induction Period/Re-Induction Period + Maintenance Period ABBV-154 (SA-INMN population): TEAEs for "Induction Period/Re-Induction Period + Maintenance Period ABBV-154" (SA_INMN) are defined as events that begin either on or after the first dose of ABBV-154 in the Induction Period/Re-Induction Period and until (i) within 70 days after the last dose of study drug in the study, or (ii) initiation of ABBV-154 rescue therapy, whichever is earlier.

Induction Period + Re-Induction Period + Maintenance Period ABBV-154 (SA-IN2MN population): TEAEs for "Induction Period + Re-Induction Period + Maintenance Period ABBV-154" (SA-IN2MN) are defined as events that begin either on or after the first dose of ABBV-154 in the Induction Period and until (i) within 70 days after the last dose of study drug in the study, or (ii) initiation of ABBV-154 rescue therapy, whichever is earlier.

If an incomplete onset date was collected for an adverse event, the event will be assumed to be treatment-emergent unless there is other evidence that confirms that the event was not treatment-emergent (e.g., the event end date was prior to the study drug start date). The number and percentage of subjects experiencing treatment-emergent AEs will be summarized.

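### SAP 10.2.4 runs exposure to last dose + 70 days although 10.2.1 stops counting events earlier, so Induction event rates per 100 patient-years come out up to 40% too low

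*SAP*

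**What the plan says.** SAP 10.2.4 defines the event rate as 100 times the number of treatment-emergent adverse events (TEAEs) divided by total patient-years, where patient-years are summed study drug exposure. The exposure rule is general: "The study drug exposure for each safety population is defined as last dose date plus 70 days, minus the first dose date". One exception follows: "For SA-All154 safety population, the duration when subjects on Placebo will not be included in the calculation".

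SAP 10.2.1 sets the period over which events count, separately for each population:

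- **Induction (SA1).** The window closes at the earliest of "the first dose of study drug in the Re-Induction Period (if applicable), or (ii) until first dose of study drug in the Maintenance Period" and 70 days after the last Induction dose.
- **Re-Induction (SA2) and Induction plus Re-Induction (SA-IN2).** The window likewise closes at the first Maintenance dose if that comes first.
- **Maintenance (SA3).** The end is either 70 days on from the last blinded dose or the start of rescue, in the SAP's words: "the last dose administration of the blinded study drug in the Maintenance Period, or (ii) initiation of ABBV-154 rescue therapy, whichever is earlier".
- **Combined sets that include Maintenance (SA-INMN, SA-IN2MN).** The limit is "within 70 days after the last dose of study drug in the study, or (ii) initiation of ABBV-154 rescue therapy, whichever is earlier".
- **All ABBV-154 (SA-ALL154).** The window covers events between "first dose of ABBV-154 and within 70 days after the last dose of ABBV-154 in the study", with events on placebo left out.

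The rates are planned output. SAP 10.2.2 says: "The number of TEAEs reported, the total number of years of study drug exposure, and the TEAE rate per 100 patient-years will be presented". SAP 10.2.4 and 10.2.6 extend them to system organ class, preferred term and adverse events of special interest (AESIs).

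**The concern.** A rate per patient-year is interpretable only if every day in the denominator is a day on which an event could enter the numerator. For any subject who moves to the next period or is rescued, the two sections break this link. The surplus days cannot hold a countable event for that period, and for a subject who rolls over they are counted again as exposure in the next period.

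In Induction this is the normal path. Protocol 4.1 sends Week 12 responders to Maintenance and non-responders to Re-Induction, so almost every completer is affected. At stake are the absolute TEAE and AESI rates, the figures a reader would set against other trials. The error runs in the reassuring direction. It also differs by period: large in Induction, absent for unrescued Maintenance subjects. Rates from different periods of this trial are therefore not comparable either.

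The version history suggests an oversight. SAP version 2.0 added the rescue cut-off to the 10.2.1 windows, but the only change it lists for the exposure calculation in 10.2.4 concerns SA-ALL154.

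**Working it through.** **Inputs**

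- Last Induction dose at Week 10, day 70 after first dose. Induction Group 4 receives placebo at that visit (SAP 2.2).
- Next period starts at Week 12, day 84 (SAP 2.2).
- Last Maintenance dose at Week 38; rescue possible from Week 4 (SAP 2.2).
- Planned total 265, or 53 per group (SAP 2.4).
- No early-stopping, roll-over or rescue shares are given in the documents. All such shares below are assumed.

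**Timing check.** The documents state no patient-year total or event rate, so the dosing calendar is checked first. The duration rule in SAP 6.0 ("Duration of treatment is defined for each subject as last dose date of blinded study drug minus first dose date + 14") gives 70 + 14 = 84 days for Induction and 38 × 7 + 14 = 280 days for Maintenance. Both equal the top duration categories in 6.0. The three periods give (12 + 12 + 40) × 7 = 448 days, the maximum in the Protocol synopsis.

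**SA1, on-schedule completer who continues**

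- Countable days: 84.
- Denominator days: 70 + 70 = 140.
- Surplus: 56 days. Factor: 84/140 = 0.60.

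For 265 such subjects:

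- at risk: 265 × 84/365.25 = 60.9 patient-years;
- counted: 265 × 140/365.25 = 101.6 patient-years;
- surplus: 265 × 56/365.25 = 40.6 patient-years.

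For one arm of 53 with an assumed 50 events, 20.3 patient-years gives 246 per 100 patient-years as planned. The matched 12.2 patient-years gives 410.

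**SA1 with early stopping.** A subject who stops at Week 4 has 28 + 70 = 98 days in both numerator and denominator. With share q stopping then, the factor is [(1 − q) × 84 + q × 98] / [(1 − q) × 140 + q × 98].

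| q (assumed) | Factor | Rate too low by |
|---|---|---|
| 0% | 0.600 | 40% |
| 5% | 0.614 | 39% |
| 10% | 0.629 | 37% |
| 20% | 0.660 | 34% |

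If one arm has 5% early stopping and another 20%, their rate ratio is distorted by 0.660/0.614 = 1.07. With equal shares it is not distorted.

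**SA2.** Subjects who do not roll over are consistent at 140 days. With roll-over share r the factor is 1 − 0.4r: 0.88, 0.80 and 0.72 for r = 30%, 50% and 70% (assumed).

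**SA-IN2, subject who enters Maintenance.** If last dose means the last Re-Induction dose, the factor is (84 + 84)/(84 + 70 + 70) = 168/224 = 0.75. If it means the last dose in the study, a subject completing Maintenance contributes 84 + 84 + 266 + 70 = 504 days, and the factor is 168/504 = 0.33.

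**SA3, last dose read as last blinded dose.** An unrescued completer has 38 × 7 + 70 = 336 days in both. A subject rescued at Week R has 7R countable days against 7R − 14 + 70 = 7R + 56 counted. With share p rescued, other drop-out ignored, the factor is [(1 − p) × 336 + p × 7R] / [(1 − p) × 336 + p × (7R + 56)].

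| Rescue week | Placebo p | ABBV-154 p | Placebo factor | ABBV-154 factor | ABBV-154/placebo ratio inflated by |
|---|---|---|---|---|---|
| 24 | 30% | 20% | 0.944 | 0.964 | 1.02 |
| 12 | 50% | 20% | 0.882 | 0.962 | 1.09 |
| 8 | 60% | 20% | 0.833 | 0.962 | 1.15 |

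Equal shares and timing give 1.00.

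**Sets without the conflict.** For rescue therapy (SA-RES), events and exposure both run to last dose + 70 days. For SA-ALL154, the natural reading ends both 70 days after the last ABBV-154 dose and excludes placebo from both.

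**The case against.** The strongest reply is that little turns on these rates. They are descriptive, and no test or decision rule in the documents uses them. All five arms share the same 12-week Induction, so the planned percentages of subjects already support the between-arm comparison. The 10.2.4 rule also fits the overall TEAE definition in Protocol 7.7, which runs to 70 days after the last dose; the conflict is with the SAP's own period-specific windows. All of that stands and limits the importance of the point. It does not make the period-specific rates right: they pair a truncated numerator with an untruncated denominator.

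Second, nowhere does the SAP add patient-years across SA1, SA2 and SA3, so the double counting harms no planned output beyond the mismatch itself. This also stands.

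Third, the figures outside SA1 and SA2 depend on what last dose means and on assumed rescue patterns. True, but the other readings enlarge the error. If rescue doses count in SA3, the 50% against 20% example at Week 12 becomes 210/336 = 0.625 against 285.6/336 = 0.85, an inflation of 1.36 rather than 1.09. Rescue at Week 4 instead of Week 8, with 60% against 20%, gives 151.2/184.8 = 0.818 against 274.4/285.6 = 0.961, an inflation of 1.17.

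Fourth, 40% is a nominal-schedule ceiling that requires every subject to complete and roll over on time. This is correct, and the early-stopping figures show how far it falls. If the next period's first dose fell on day 81 to 87 (assumed, since the documents reviewed give no visit window), the figure for a completer would be 42% to 38%.

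Finally, consistency in SA-ALL154 is inferred: 10.2.4 does not say whether the 70 days after a last placebo dose are removed.

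**Conclusion.** The concern holds. As written, 10.2.4 and 10.2.1 give different end dates for every subject who rolls over or is rescued, and nothing elsewhere in the documents truncates exposure.

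- **Induction:** absolute rates are 40% too low on the nominal schedule with everyone continuing, and 34% to 37% too low with 10% to 20% stopping at Week 4 (assumed). Ratios between arms are close to unaffected unless early stopping differs by arm.
- **Re-Induction:** rates are 12% to 28% too low for roll-over shares of 30% to 70% (assumed).
- **Maintenance:** the surplus is 56 days per rescued subject on the blinded-dose reading. If placebo subjects are rescued more often, the placebo rate is understated more and ABBV-154 looks relatively worse, by 1.02 to 1.15 times over the tabulated scenarios.

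Numbers and percentages of subjects are untouched. This should be corrected before the period safety tables are produced, but it does not threaten the efficacy analysis or any formal comparison.

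**What to change.** In SAP 10.2.4, define exposure as E minus first dose date, with no + 1, where E is the earliest of:

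- the first dose date of the next period, for populations whose 10.2.1 window closes there;
- the date of the first ABBV-154 rescue dose, for populations whose 10.2.1 window closes there;
- the last dose date + 70 days.

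Day E itself is not counted, so the last counted day for a roll-over or rescued subject is the day before the next period or rescue begins. An on-schedule Induction completer then contributes 84 days, and no day falls in two periods. Subjects followed to last dose + 70 days keep their present count.

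State that last dose is period-specific, with last blinded dose for SA3 as in 6.0 and 10.2.1. For the combined sets, say that exposure ends on the date that closes the population's 10.2.1 window. Keep the placebo exclusion for SA-ALL154, and state that it covers the 70 days after a last placebo dose.

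The core change costs one SAP sentence and one derivation line, plus these clarifications, and needs no new data. Reported absolute rates will be higher, and patient-years of successive periods will no longer overlap.
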